4.3.2 Microbiome stool collection

For microbiome analyses, *T. trichiura* positive samples as well as 100 STH negative controls (in up to 2 stool samples each at baseline and 14-21 days after treatment) will be analyzed. For this purpose, 1-2 g of freshly collected samples will be suspended in 15 mL of sterile phosphate buffer supplemented with 0.1% L-cysteine (PBSc) in a sterile 50 mL falcon tube. The tubes will be left for 5 minutes to let insoluble particles settle. 1 mL aliquots (up to 2 aliquots) of the supernatant will be transferred to sterile cryogenic vials, supplemented with 1 mL of 40% glycerol solution, and subsequently frozen (at -20°C) until shipment to Swiss TPH in Switzerland is arranged for subsequent molecular and microbiological

analyses. For the microbiome analysis additional data on height and weight of participants will be collected.

4.3.3 Blood type determination

For various infectious diseases the association between blood type and susceptibility to infection as well as infection intensity has been studied [19, 20]. However, there is very limited evidence on this relationship in STH infections, particularly in *T. trichiura* [21]. To investigate the potential association between blood type and *T. trichiura* infection intensity all enrolled participants will be asked to provide a finger-prick blood sample at baseline. Blood type will be determined performing an ABO agglutination test (e.g., using DiaClon/BioRad ID-cards or commercial antisera A, B and D).

4.3.4 Clinical examination

A clinical examination of the study participants assessing general health, anthropometric parameters including height and weight as well as temperature using a non-contact infrared forehead thermometer (Braun No touch – NTF3000; Braun, Kronberg, Germany) will precede the treatment. Each participant will be asked to provide a finger-prick sample to measure hemoglobin (Hb) levels, which will be detected using a HemoCue analyzer (Hb 301 system, Angelholm, Sweden), and to determine blood type (see section 4.3.3). A venous blood sample (approximately 4 ml) will be taken at baseline to assess biochemical parameters, such as urea, creatinine, bilirubin, azotemia, Alanine Amino Transferase (ALAT), Aspartate Amino Transferase (ASAT), as well as blood cell counts (e.g. hematocrit, erythrocytes and platelets). Results from baseline biochemical analysis may be reported back to participants during the trial period as seen fit. To avoid accidental treatment of pregnant girls/women all female participants will be asked to provide a urine sample to be subjected to a pregnancy RDT during clinical examination and the day of treatment administration. Before treatment is administered, each participant will be asked to provide a finger-prick blood sample for a rapid diagnostic test (RDT) for *Plasmodium* spp. infection. All trial participants will further be asked about existing clinical symptoms before drug administration using a standardized questionnaire.

4.3.5 Adverse events assessment

Participants will be monitored at the site for 3 hours after treatment administration to observe any possible acute AEs and reassessment will be done at 24h post-treatment. Additionally, interviews will be conducted to determine the emergence of clinical symptoms such as headache, abdominal pain, itching, nausea, vomiting and diarrhea directly before treatment within the scope of baseline assessment. At 3 and 24 hours after treatment and retrospectively at days 14 – 21, participants will again be interviewed for the assessment of AEs. Symptoms arising within the timespan of 24 hours after treatment and the respective follow-up time points will be monitored passively by teachers or local health workers who will report incidences to the study team. Any symptoms will be recorded in the designated case report form (CRF) and immediate action will be undertaken if indicated.

4.3.6 Assessment of efficacy after treatment

The efficacy of the treatment will be determined 14-21 days post-treatment by collecting another two stool samples, which will be microscopically examined for *T. trichiura* using duplicate Kato-Katz thick smears. Participants will be considered cured if no *T. trichiura* eggs are found in the follow-up stool samples. Eggs per gram will be assessed by adding up the egg counts from the quadruplicate Kato-Katz thick smears and multiplying this number by a factor of six. Geometric and arithmetic mean egg counts will be calculated for the different treatment arms before and after treatment to assess the corresponding ERRs. At the end of the study all participants remaining positive for *T. trichiura* infection will be treated with the currently best recommended treatment of repeated doses of mebendazole (100 mg twice daily over 3 days).

4.3.7 Pharmacokinetic studies

The pharmacokinetic and exposure-response correlation study will be performed in a maximum of 14 adolescents (aged 12-20 years) in the two treatment arms receiving either ivermectin/albendazole or albendazole. The absorption of all study drugs is known to be better after consumption of a high-fat meal, therefore PK participants will receive a local high-fat breakfast before treatment [22]. Since PK population parameters of all study drugs are available [23], a sparse sampling approach can be applied to describe the PK profiles of the individual drugs upon administration as well as a potential interference between ivermectin and albendazole upon co-administration. Within a sparse sampling approach, instead of describing the PK profile for each participant separately, samples are allocated to different time points and/or individuals within the same treatment. Statistical inferences are performed to characterize the population-based PK profile of a specific treatment arm. This approach allows for a reduced number of samplings per treatment arm and renders a PK characterization well tolerable. To this end, a small drop of blood from the fingertip will be taken for a maximum of 8 finger pricks per participant. In total only 14 participants (7 per treatment arm) will undergo PK. The exact time points will cover a timespan of 0 to 24 hours after treatment and will have to be adapted according to a PK model of ivermectin and albendazole currently developed based on data gathered during recent trials involving these study drugs [24, 25]. Capillary blood ($\leq 60 \mu\text{L}$, i.e. $10 \mu\text{L}$ for albendazole, and a drop of blood ($\sim 60 \mu\text{L}$) for ivermectin) will be collected by puncture with a finger prick. Two microsamples (duplicates) will be taken with one finger prick. Each time, the drop of blood ($10 - 60 \mu\text{L}$) will be directly transferred on Mitra® sticks (albendazole) or dried-blood spot cards (ivermectin) [26]. The dried sticks and filter paper will be transported to Swiss TPH, Basel, and stored at room temperature until analysis (< 2 months post-treatment). The quantification of the study drugs will be performed using the validated liquid chromatography tandem mass spectrometry (LC-MS/MS) method as described elsewhere [23, 26]. Drug concentrations will be calculated by interpolation from a calibration curve with a lower limit of quantification of 1-5 ng/ml. 7% of the sample duplicates will be analyzed for quality control, and the measured concentrations will be used to determine between-run and overall precision and accuracy of the analysis.

From the 14 PK participants whole genome sequencing will be used to determine associations between pharmacogenetic variants with pharmacokinetic or pharmacodynamic parameters. One blood sample (1 ml) for pharmacogenomics will be aliquoted from the venous blood sample collected at enrolment (as described above (4.3.4 clinical examination). Whole blood (1.5 ml) will be dispensed into an EDTA coated tube, inverted six times to mix anticoagulant thoroughly, and transferred by pipette to a cryovial and frozen. Samples will be analyzed at the University of Helsinki in Finland.

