Study Objectives	
Our primary objective is to demonstrate superiority of
 
 a) Arm A: moxidectin (8 mg) / albendazole (400 mg) combination, compared to b) Arm B: albendazole (400 mg) 
in terms of cure rate (CR) against T. trichiura infections in adolescents and adults aged 12-60 years assessed at 14-21 days post-treatment by Kato-Katz microscopy.
 
The secondary objectives of the trial are:
 
 a) to determine the egg reduction rates (ERRs) of moxidectin/albendazole combination therapy compared to albendazole monotherapy against T. trichiura b) to determine the CRs and ERRs in T. trichiura-infected participants given combined ivermectin (200 µg/kg) and albendazole (400 mg) compared to those given albendazole monotherapy c) to determine the CRs and ERRs of the study drugs against Ascaris lumbricoides and hookworm in co-infected participants d) to evaluate the safety and tolerability of the treatment e) to characterize population pharmacokinetics (popPK) and drug-drug interactions of the study drugs albendazole and ivermectin in combination with albendazole in T. trichiura infected individuals (aged 12 to 20 years) f) to assess the effect of the gut microbiota on pharmacokinetics parameters and treatment outcome (CRs and ERRs) g) to assess drug-specific off-target effects of anthelmintic treatment on gut microbial communities in post-treatment samples h) to assess the pharmacogenomics of ivermectin and albendazole using whole genome sequencing 
The exploratory objective of this trial is to assess the association between T. trichiura infection intensity and blood type.

Study design	Parallel randomized controlled superiority trial
Study product / intervention	Administration of a single oral dose of moxidectin (8 mg) / albendazole (400 mg) or a single dose of ivermectin (200 µg/kg) / albendazole (400 mg)

Comparator(s)	Albendazole (400 mg)

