4.4 Measure to minimize bias

Study participants eligible for treatment will be randomly assigned to one of the three treatment arms using a computer-generated stratified randomization code. The random allocation sequence with block sizes that will be a multiple of 3 and stratified by 2 levels of infection intensity at screening (light: 1-999 EPG, and moderate plus heavy: ≥ 1000 EPG *T. trichiura* infections) will be provided by a statistician. This way, all treatment arms will have a similar proportion of participants with light infection intensity. Allocation concealment will be warranted using sequential, opaque, sealed envelopes. In the case of accidental unblinding or necessary code breaks, the sponsor will be immediately notified (within 24 hours) and data will be analyzed as set forth in section 8.3. Treatment arm A and B will be double blinded (*i.e.* study participants and the trial team/researchers conducting the treatment and assessing the outcomes will be blinded) using tablets and appearance-matched placebos in bottles relabeled with the respective arm (*i.e.* A or B) by investigators not involved in efficacy assessment of the trial. Treatment arm C (receiving ivermectin/albendazole) will be an open, unblinded group.

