5.5 Treatment of participants

After randomization, all eligible participants will be treated with the respective single or combination treatment regimen according to their assigned treatment arm at day 0. Albendazole will be the product of Glaxo Smith Kline (Zentel®) and a single tablet of 400 mg will be administered. Moxidectin tablets and matching placebo tablets (in terms of appearance) will be obtained from Medicines Development

for Global Health (MDGH), Australia, and four tablets of 2 mg will be administered. Ivermectin tablets (3 mg) will be obtained from Merck (Stromectol®), and administered at a dose of 200 µg/kg based on the recorded body weight of each participant.

The tablets will be handed out from 4 drug containers (moxidectin, ivermectin, placebo and albendazole) according to the randomization list. Each person will receive either:

- (i) A single tablet of albendazole plus four tablets of moxidectin
- (ii) A single tablet of albendazole plus four tablets of placebo
- (iii) A single tablet of albendazole plus 200 µg/kg of ivermectin

All drugs will be administered in the presence of the PI and/or co-PI, and ingestion confirmed. This will be recorded with the time and date of dosing. Participants will be asked to limit the use of any drugs other than those prescribed by the study medical team for the duration of the study as described in section 5.6. After ingestion of the medication, the subjects will be observed for 3 hours to ensure retention of the drug. Vomiting within 1 hour post-dosing will require re-dosing. The subjects will not be allowed more than one repeated dose. No re-administration will be needed for subjects vomiting after one hour. The PI or the co-PIs are responsible for drug accountability at the study site. Maintaining drug accountability includes careful and systematic study drug storage, handling, dispensing, and documentation of administration. Prior to administration, drugs will be stored at room temperature and protected from light and exposure to moisture in a secure area with limited access at the study site.

A study physician will do capillary blood sampling (finger pricking) for the population PK assessment for a maximum of 14 study participants (maximum of 7 adolescents in each of two treatment arms involved in PK) in a quiet location in the community.

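### PK sampling takes place in only one arm of the blinded pair, so up to 7 of 94 arm B participants are identifiable as albendazole alone

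*Combined protocol and SAP*

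**What the plan says.** Section 4.3.7 places the PK substudy "in the two treatment arms receiving either ivermectin/albendazole or albendazole". It gives the number as "In total only 14 participants (7 per treatment arm) will undergo PK", and section 5.5 agrees. PK participants are willing adolescents aged 12 to 20, each giving at most eight finger-prick samples between 0 and 24 hours.

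The same section gives a reason for the meal, "The absorption of all study drugs is known to be better after consumption of a high-fat meal", and continues: "therefore PK participants will receive a local high-fat breakfast before treatment". Section 5.5, which describes dosing for everybody, gives no food condition.

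On blinding, section 4.4 says "Treatment arm A and B will be double blinded", and extends this to participants, treating staff and outcome assessors. It adds: "Treatment arm C (receiving ivermectin/albendazole) will be an open, unblinded group". Bottles are relabelled with one letter per arm by investigators who take no part in efficacy assessment. The synopsis identifies arm A as moxidectin/albendazole and arm B as albendazole alone.

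Section 8.3 makes the primary comparison by unadjusted logistic regression in all participants with endpoint data, followed by a per-protocol analysis. It has no analysis that separates PK participants and no specific rule for unblinded participants, although section 4.4 refers to it for that purpose.

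**The concern.** A procedure that everyone present can see takes place in one arm of a blinded pair and not in the other. Anyone who knows the protocol and sees a blinded participant given the breakfast or sampled repeatedly can work out the treatment. Because bottles carry one letter per arm, a single such participant could also show what the letter B means for the rest of that arm.

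The blinded assessment of tolerability, a secondary endpoint, is the most exposed. The PK window of 0 to 24 hours contains the active adverse event interviews at 3 and 24 hours. Section 5.5 has a study physician take the PK samples and section 6.2 has the study physician judge adverse event intensity. Nothing separates the two tasks.

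Food is a second, smaller matter. If the others are dosed without a comparable meal, part of arm B has a pre-dose condition that nobody in arm A has, in the one comparison the trial is powered for.

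**Working it through.** **Blinding.** Setting the sections side by side:

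1. PK participants are in B (up to 7) and C (up to 7), and there are none in A (4.3.7, 5.5).
2. C is open, and A and B are the blinded pair (4.4).
3. A PK participant in the blinded pair is therefore in B. This follows from the finger pricks alone; the breakfast is a second, earlier sign of the same thing.
4. The breakfast precedes dosing, so someone must know the assignment before treatment in order to fill the arm B places. Section 4.4 does not say who.

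Share of arm B: 7/94 = 7.4% of those recruited, or 7/85 = 8.2% of evaluable participants if all seven are retained.

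**The plan's own power.** Inputs from section 8.2: cure rates 10% and 30%, two-sided 5%, 85 per arm, 90% power. With the pooled normal approximation:

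- SE under no difference = √(2 × 0.20 × 0.80 / 85) = 0.0614
- SE under the alternative = √((0.09 + 0.21) / 85) = 0.0594
- z = (0.20 − 1.96 × 0.0614) / 0.0594 = 1.34, so power = 91.0%

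The stated 90% is reproduced.

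**Possible effect of food on A versus B.** The documents give no cure rate for albendazole after a meal, so the fed rate p is assumed. Arm B cure rate = (78 × 0.10 + 7 × p) / 85, with all seven retained and arm A at 30%.

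| Assumed p in the seven | Arm B cure rate | Difference from A | Power |
|---|---|---|---|
| 10% (no effect) | 10.0% | 20.0 points | 91.0% |
| 15% | 8.85/85 = 10.4% | 19.6 points | 89.6% |
| 20% | 9.20/85 = 10.8% | 19.2 points | 88.0% |
| 30% | 9.90/85 = 11.6% | 18.4 points | 84.4% |

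The last row supposes that a meal makes albendazole alone as effective as the planned combination, so it is a generous upper case.

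**Cost of leaving the seven out.** With 78 in B and 85 in A:

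- pooled rate = (7.8 + 25.5) / 163 = 0.204
- SE under no difference = √(0.204 × 0.796 × (1/78 + 1/85)) = 0.0632
- SE under the alternative = √(0.09/78 + 0.21/85) = 0.0602
- z = (0.20 − 1.96 × 0.0632) / 0.0602 = 1.26, so power = 89.7%

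**C versus B.** Each arm has up to seven fed participants, so the numbers are balanced and no food correction is called for.

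**The case against.** The strongest case on the other side is that little of this reaches the primary endpoint. Cure is the absence of eggs on slides read by technicians, with 10% re-read (4.3.1). Egg-count sheets and PK time records are listed as separate source documents (7.1), and nothing says that the readers know PK status. This stands: the documents do not show that egg counts are compromised.

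A reader might infer that the whole comparator is fed differently and can be identified. The documents do not support that. At most seven people are directly affected, and the other 87 or more in arm B fall under the same text as arm A. That only PK participants are fed is itself read from silence, since no section says that the others fast.

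A reader might also infer that the meal biases the primary result in favour of the combination. Section 4.3.7 speaks of absorption, and no section links albendazole exposure to cure. If better absorption did raise cure, arm B would look better and the difference would shrink.

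The bottle letter is a risk and not a finding. The documents do not say who sees both the bottle and the PK sampling. If bottle letters match the arm names in the synopsis, anyone holding the protocol already knows what they mean. Likewise, the PK sampler and the adverse event grader share a role but need not be the same person: section 9.3 lists three local physicians, and section 6.1.1 also allows a nurse to grade.

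Finally, leaving out PK participants removes willing 12 to 20 year olds from B with no counterpart removed from A. That is a real limitation of the sensitivity analysis, and the plan should state it.

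None of this removes the conflict between sections 4.3.7 and 4.4 for the seven.

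**Conclusion.** The point holds in a limited form. The double-blind statement in section 4.4 cannot be met for up to 7 of 94 arm B participants, because PK sampling and the breakfast that goes with it mark them as albendazole alone. Identification could spread through the single bottle letter, but the documents do not establish that it would. Adverse event assessment is more exposed than the egg counts.

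A food difference between A and B is possible for these seven but is not established. Under assumed fed cure rates of 15% to 30%, it moves the arm B rate by 0.4 to 1.6 points and lowers power from 91% to between 90% and 84%. This rests on all seven being retained, on the others not receiving a comparable meal, and on absorption carrying through to cure. The direction is against superiority, so this mechanism would not produce a false claim for the combination. The point merits correction because the plan contradicts itself on blinding and the remedy is cheap.

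**What to change.** 1. Reconcile sections 4.3.7, 4.4 and 5.5 on blinding and on the pre-dose food condition. The sponsor decides the condition. State in 4.4 that PK participants in arm B are not fully blinded.
2. Have the staff who relabel the bottles, and who are not involved in efficacy assessment, make and hold the PK selection. Keep PK status and bottle letters from stool readers and, where feasible, from those who grade adverse events. This cannot hide PK status from the participants themselves or from staff present at sampling.
3. Add to section 8.3 a prespecified sensitivity analysis of A versus B, for cure rate and adverse events, without PK participants. Preferably also restrict it or adjust it by age, and say that the exclusion removes willing 12 to 20 year olds from B only, so it is not a fully randomised comparison. A matching exclusion for C versus B is not needed on food grounds.

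The cost is protocol wording, a task for existing staff and one extra analysis with about one point less power (91% to 90%). The primary analysis and the sample size are unchanged.

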4.4 Measure to minimize bias

Study participants eligible for treatment will be randomly assigned to one of the three treatment arms using a computer-generated stratified randomization code. The random allocation sequence with block sizes that will be a multiple of 3 and stratified by 2 levels of infection intensity at screening (light: 1-999 EPG, and moderate plus heavy: ≥ 1000 EPG *T. trichiura* infections) will be provided by a statistician. This way, all treatment arms will have a similar proportion of participants with light infection intensity. Allocation concealment will be warranted using sequential, opaque, sealed envelopes. In the case of accidental unblinding or necessary code breaks, the sponsor will be immediately notified (within 24 hours) and data will be analyzed as set forth in section 8.3. Treatment arm A and B will be double blinded (*i.e.* study participants and the trial team/researchers conducting the treatment and assessing the outcomes will be blinded) using tablets and appearance-matched placebos in bottles relabeled with the respective arm (*i.e.* A or B) by investigators not involved in efficacy assessment of the trial. Treatment arm C (receiving ivermectin/albendazole) will be an open, unblinded group.

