6.2 Methods of recording and assessing adverse events

Few adverse events have been reported following albendazole, ivermectin or moxidectin administration in STH-infected individuals. The most common adverse events were abdominal cramps, headache, fatigue, nausea, diarrhea, fever and vertigo [7, 15, 29-32].

The observation time for AE starts when the treatment is initiated. Subjects will be observed for at least 3 hours following treatment for any acute AE and reassessment will be done at 24h post-treatment. If there is any abnormal finding, the local study physician will perform a full clinical examination and findings will be recorded. An emergency kit will be available on site to treat any medical conditions that warrant urgent medical intervention. Participants will also be interviewed at 3h and 24h actively as well as retrospectively 14 -21 days after treatment about the occurrence of AEs. Any potential AEs happening between 24 hours and the follow-up time point (14-21 days) will be monitored passively and managed with the help of the locally based medical team (including specifically trained community health workers, nurses and medical doctors). Medical intervention will be provided if necessary.

Information on all AEs (incidence, intensity, seriousness and causality) will be entered immediately in the source document, and also in the appropriate AE module of the case report form. For all AEs, sufficient information will be pursued and/or obtained so as to permit i) an adequate determination of the outcome of the event (i.e. whether the event should be classified as a SAE); and; ii) an assessment of the causal relationship between the AE and the study treatments. Intensity of AE will be judged by the study physician, following guidelines by the European Medicine Agency (Note for Guidance on Clinical Safety Data Management).

All SAEs, unexpected adverse drug reactions or SUSARs must be reported as described in Section 6.3.

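### Staff blinding in arms A and B is not secured: the bottle letter is the published arm name, and PK sampling identifies albendazole-alone participants to staff who grade adverse events

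*Combined protocol and SAP*

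**What the plan says.** **Blinding and labels.** Section 4.4 describes arms A and B as double blind, covering participants, the staff who give treatment and those who assess outcomes. The means is "appearance-matched placebos in bottles relabeled with the respective arm", that is, A or B. The people who relabel must take no part in judging efficacy; adverse event (AE) assessment is not named. Arm C, ivermectin/albendazole, "will be an open, unblinded group".

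**Meaning of the letters.** The synopsis (Study Objectives) gives it: "Arm A: moxidectin (8 mg) / albendazole (400 mg) combination, compared to b) Arm B: albendazole (400 mg".

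**PK sampling.** Section 4.3.7 places it "in the two treatment arms receiving either ivermectin/albendazole or albendazole". It adds: "In total only 14 participants (7 per treatment arm) will undergo PK". Each sampled participant has up to 8 finger pricks over 0 to 24 hours. The section also says that "PK participants will receive a local high-fat breakfast before treatment".

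**Who samples and who grades.** Section 5.5: "A study physician will do capillary blood sampling (finger pricking) for the population PK assessment". Section 6.2: "Intensity of AE will be judged by the study physician". Section 6.1.1 allows grading by a physician or a nurse of the trial. Section 6.1.2 bases relatedness partly on what the treatment is already known to cause, and does not say who judges it. Section 9.3 lists three local physicians, one of whom is the local PI.

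**The concern.** Section 4.4 states an aim (blinded staff), and two features of the plan work against it.

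First, a bottle letter masks treatment only if those who see it do not know what it stands for. Here it is the arm name used in the protocol. Section 5.5 has dosing take place in front of the PI or a co-PI, who know the protocol.

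Second, PK sampling is a visible procedure that occurs in only one of the two blinded arms. It marks those participants as albendazole alone, whatever is printed on the bottle.

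AEs are a secondary endpoint. They are actively captured at 3 and 24 hours, within the PK sampling window. Severity and relatedness are staff judgements. A grader who knows whether the four extra tablets were moxidectin or placebo may judge the same symptom differently. AEs are compared descriptively (synopsis, Statistical Analyses), so no planned analysis would reveal or correct such a shift.

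**Working it through.** **Step 1. Is the letter a code?** Section 4.4 labels the bottles with the arm, A or B. The synopsis defines A as moxidectin/albendazole and B as albendazole alone. Section 4.4 then uses C for ivermectin/albendazole, which continues the same series. The natural reading is that the bottle letter is the published arm letter. No further inference is needed to decode it.

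**Step 2. What does PK status reveal?** PK is sampled in ivermectin/albendazole and albendazole alone, not in moxidectin/albendazole. Arm C is open, so staff know who is in it. A PK participant outside arm C is therefore in arm B. Inputs: 7 PK participants per arm (4.3.7), 94 recruited per arm (8.2), 188 in arms A and B together (4.3).

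- Share of arm B: 7/94 = 7.4%.
- Share of the blinded comparison: 7/188 = 3.7%.

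Unless the breakfast is given more widely than described, someone must also use the allocation of these 7 before dosing. The documents do not say who.

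**Step 3. How do the two leaks combine?** With one letter per arm, a staff member who links one of the 7 to a bottle learns the meaning of B, and of A by elimination. That covers all 188. So even if the letters were secretly scrambled, PK sampling could decode them.

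**Step 4. Would several codes per arm be enough?** The documents give no number of codes; k = 5 and k = 10 per arm are my assumptions. Suppose the 7 are a random draw without replacement from the 94, and code i covers n_i participants. The chance that code i has at least one PK participant is

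1 − C(94 − n_i, 7) / C(94, 7).

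Summing this over codes gives the expected number decoded. Weighting each term by n_i gives the expected number of participants exposed.

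| Codes in arm B | Group sizes | Chance per code | Codes decoded (expected) | Participants exposed (expected) |
|---|---|---|---|---|
| 1 | 94 | 1 | 1 | 94 (100%) |
| 5 | 19, 19, 19, 19, 18 | 0.806 (n = 19), 0.786 (n = 18) | 4.01 | 75.4 (80.2%) |
| 10 | four of 10, six of 9 | 0.557 (n = 10), 0.518 (n = 9) | 5.34 | 50.3 (53.5%) |
| 94 (one per participant) | 1 each | 7/94 = 0.074 | 7 | 7 (7.4%) |

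PK participants are volunteers aged 12 to 20, so the draw may not be random over codes. If the 7 clustered, as few as 1 code could be decoded; at most it would be 5 of 5, or 7 of 10. Several codes per arm thus reduce the leak but do not close it for someone who sees both code and PK status. Keeping those two pieces of information away from AE graders does most of the work.

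**Step 5. Can a grader hold this information?** Section 5.5 gives PK sampling to a study physician and section 6.2 gives AE intensity to the study physician. Section 6.1.1 adds nurses as possible graders. With three local physicians, sampler and grader may be different people, but no passage requires it.

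**The case against.** Much can be said against a serious consequence.

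- **Albendazole is in both arms.** Section 6.2 gives one common list of AEs for the three drugs. Section 6.1.2 offers only two categories, possibly related and unrelated, and the second needs a reasonable alternative explanation. A grader who knows the extra tablets were placebo still knows that albendazole was given, so a typical symptom would usually remain possibly related. This stands and limits the relatedness route.
- **Symptoms come from participants.** AEs are elicited by interview, and grades 1 to 3 in section 6.1.1 rest on what the participant experiences. Tablets match in number and appearance, and nothing shows that participants are unblinded. This stands: AE incidence is largely spared.
- **The role overlap is only possible.** Sampler and grader may differ, a nurse may grade, and section 5.5 puts PK sampling in a quiet place. This also stands, but a quiet place does not separate staff.
- **PK adds little if the letters are already decoded.** True for the letters as they now are. PK matters for the 7 themselves, and once the letters are replaced.

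A reader might infer that the whole A versus B safety comparison is compromised, or that cure rate is biased. The documents do not support either. Nothing shows that Kato-Katz readers see bottle letters or PK status. A reader might also take the container names in section 5.5 as proof of unmasked dispensing, but they may simply describe contents. Section 4.4 also refers to section 8.3 for data after unblinding, and 8.3 has no such rule. The available-case intention-to-treat analysis already keeps those participants, however, so this point does not rest on that gap.

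**Conclusion.** The concern holds as a gap between what section 4.4 promises for staff and what the labelling and PK plan deliver. The bottle letter decodes treatment for anyone who knows the protocol. PK sampling independently identifies 7 of 94 arm B participants, and through a shared letter one of them can decode the allocation of all 188.

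The exposed outcome is staff judgement of AE severity and relatedness, if those who grade also see the bottle letter or PK status. The plan does not prevent that, but does not say that it happens. The documents do not allow the size of any AE bias to be estimated.

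The textual facts are firm; the step from them to biased AE grading is only possible. I place the point between minor and should-fix. The case for acting is that the remedy is cheap and the trial claims double blinding for this comparison.

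**What to change.** 1. **Section 4.4.** Replace A and B on the bottles with random codes that the protocol does not decode: either participant-level numbers or several codes per arm. The statistician holds the key. Extend the exclusion of the relabelling investigators from efficacy assessment to AE assessment as well.
2. **Sections 4.3.7, 5.5, 6.1.1 and 6.2.** State that the key holder picks the albendazole-alone PK participants. State also that no physician or nurse who takes PK samples, or who sees both bottle codes and PK status, grades severity or relatedness of AEs in arms A and B.

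Part 2 is needed whichever coding is chosen. Participant-level numbers confine the leak to the 7 but do not remove it, and several codes per arm confine it less.

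**Cost.** Relabelling, one code key, and a restriction on which existing staff grade AEs. If the local PI, who is one of the three physicians, witnesses dosing and knows who is sampled, that person is barred too. With a second physician sampling, only one physician would be left to grade, plus any nurse who meets the same condition. The 7 remain recognisable to whoever samples them. Sample size, visits, eligibility and treatment do not change.
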